6.5 Waivers of Inclusion/Exclusion Criteria

No waivers of these inclusion or exclusion criteria will be granted by the investigator and the sponsor or its designee for any patient enrolling into the study.

7 DESCRIPTION OF STUDY TREATMENTS AND DOSE MODIFICATIONS

7.1 Description of Investigational Product

CO-1686 is provided as yellow, film-coated tablets for PO administration in 2 dosage strengths made from the same drug blend. The strengths are achieved by adjusting the total tablet weight. The strengths are differentiated by tablet shapes: 125 mg strength is a round tablet and 250 mg strength tablet is an oval tablet. Each tablet consists of CO-1686 HBr drug substance, silicified microcrystalline cellulose, croscarmellose sodium, colloidal silicon dioxide, copovidone, magnesium stearate and hypromellose based film coat. Excipients used are generally regarded as safe (GRAS). Tablets are packaged along with desiccant in high density polyethylene bottles closed with a child-resistant cap. Tablets will be supplied to the study sites by the sponsor. CO-1686 tablets should be stored in their original packaging at 15-30 °C (59-86 °F).

Child-resistant bottles containing CO-1686 tablets are labeled according to applicable regulations for investigational products. Patients should be advised not to split or crush tablets. Additionally, patients should be advised not to take tablets with gross visual defects such as chips. Defective tablets should be returned to the study site.

7.2 Method of Assigning Patients to Treatment Groups

All patients enrolled in the study will receive PO CO-1686.

7.3 Preparation and Administration of Protocol-specified Treatment

CO-1686 will be administered at a dose of 625 mg BID (Cohort A) or 500 mg BID (Cohort B). Patients should take CO-1686 as directed by the treating physician. Each dose should be taken with 8 oz (240 mL) of water and with a meal or within 30 minutes after a meal. Tablets should be swallowed whole.

If a patient misses a dose (i.e., does not take it within 6 hours of the scheduled time), he or she should resume taking CO-1686 with their next scheduled dose. Missed or vomited doses will not be made up.

The investigator or designee will be responsible for distributing the appropriate strength(s) of PO CO-1686 tablets to all patients. A sufficient number of tablets will be provided to the patient to last until the next scheduled visit. Patients will be instructed to record daily doses taken or not taken on a patient diary, and will be instructed to bring their CO-1686 tablets and patient diary to the next scheduled visit for reconciliation by site personnel.

7.4 Dose Modifications of Protocol-specified Treatment

No dose escalation beyond the starting dose is allowed in either cohort.

Dose reduction steps are allowed for each patient, with the overall number of dose reduction steps at the investigator's discretion. Dose reduction should be in increments of 125 mg BID

with up to 2 dose reduction steps permitted in both cohorts. Any need for further dose reduction, or adjustment from a twice to 3 times daily (TID) dosing regimen should be discussed with the sponsor before implementing. If a TID regimen is used, the total daily dose should not exceed 1,125 mg (i.e. not more than 375 mg TID).

For Grade 3 or 4 hematologic and non-hematologic toxicities (except for nausea/vomiting, alopecia, QTc prolongation and hyperglycemia), the dose should be initially reduced by 125 mg BID (to 500 mg BID, if the starting dose was 625 mg BID; or to 375 mg BID, if the starting dose was 500 mg BID). Re-escalation of dose after resolution of AEs must be discussed with, and approved by the sponsor.

Once the dose has been reduced, treatment continues at that dose level until the next visit; no dose escalation is possible between visits. If a patient continues to experience toxicity, or if dosing with CO-1686 is interrupted for > 14 consecutive days due to toxicity, treatment should be discontinued unless otherwise agreed between the investigator and the sponsor before reintroduction of study drug.

Management of prolonged QTcF

ECGs will be measured throughout the study as described in the protocol. Readings for QTcF prolongation will be based on the average seen in the ECGs for each time point. Patients are required to have within-normal-range potassium and magnesium at enrollment, and these electrolytes should be maintained within range during CO-1686 treatment, if necessary using supplementation. If QTc prolongation of National Cancer Institute (NCI) Common Terminology Criteria for Adverse Events (CTCAE)¹⁵ version 4.03 Grade 3 are observed, CO-1686 will be held until the event has improved to Grade 1. CO-1686 can then be re-started at a reduced dose upon approval by sponsor. If CTCAE Grade 3 or above QTc prolongation recurs, then CO-1686 will be discontinued unless agreed with the sponsor that additional dose reduction can be evaluated. If QTc prolongation changes of CTCAE Grade 4 are observed at any time, CO-1686 will be discontinued permanently.

Management of hyperglycemia

CO-1686 causes hyperglycemia in some patients secondary to inhibition of the insulin-like growth factor 1 receptor (IGF-1R) and insulin receptor (IR) kinases by a metabolite. Therefore, some patients will require addition of a glucose lowering medication and patients with pre-existing diabetes may require more frequent monitoring and/or adjustments of diabetic medication. Clinical experience with CO-1686 suggests hyperglycemia generally occurs within the first 3 weeks of treatment, leading to the need for more intensive glucose monitoring during the first several weeks of the study. In Phase 1/2 clinical trial experience, increased nausea and vomiting, and decreased appetite, diarrhea, muscle cramps and fatigue have been reported in patients with hyperglycemia. Such patients must be closely monitored including assessment of fasting glucose levels and early initiation of anti-hyperglycemic therapy. As CO-1686-induced hyperglycemia is mediated through insulin resistance, agents that suppress glucose synthesis (metformin), increase sensitivity to insulin (glitazones) or increase glucose excretion (sodium-glucose cotransporter 2 [SGLT2] inhibitors) are expected to be more effective than those that increase plasma insulin (sulphonylureas or exogenous insulin). Metformin has been

used most frequently in CO-1686 clinical studies and is, therefore, recommended as the initial agent to manage hyperglycemia in patients with normal renal function. In addition, preliminary data from the ongoing Study CO-1686-008 suggest that starting metformin at the same time CO-1686 therapy is initiated may prevent the development of CO-1686-induced hyperglycemia. For all patients, irrespective of whether they are receiving metformin prophylactically or therapeutically, glucose monitoring should be conducted according to the following schedule:

- Fasting glucose will be measured at the following visits: Screening, C1D1, C1D4 (± 1 day), C1D8 (± 1 day), C1D15 (± 1 day), C2D1, C2D15 (± 1 day), C3D1, C4D1, C5D1, CND1... and End-of-Treatment Visit.

The following guidelines for the for management of hyperglycemia are based on experience in the Phase 1 study. Whilst the blood glucose thresholds for intervention outlined below should be followed, management of individual patients should be based on local practices and the treating physician's judgment. In all cases, the prescribing information should be followed and the maximum approved dose of the anti-hyperglycemic agent should not be exceeded.

1. Additional monitoring outside of per protocol schedule ([Table 9-1](#)) is not needed if fasting glucose is less than 125 mg/dL (< 6.94 mmol/L).
2. If fasting glucose ≥ 125 mg/dL (≥ 6.94 mmol/L) and ≤ 160 mg/dL (≤ 8.88 mmol/L), patients will be asked to perform self-monitoring of blood glucose using finger stick blood testing (preferred choice) or urine dipstick testing (a urine dipstick can show a false-positive glucosuria in patients taking SGLT2 inhibitors). Initiation of anti-hyperglycemic therapy with metformin or anti-hyperglycemic agent of choice should be considered at this time, particularly for patients with symptoms of increased nausea, vomiting, decreased appetite, diarrhea, muscle cramps and fatigue. Tests should be performed at home once daily (QD) for at least 2 weeks, taking note of time, fasted/fed state, and glucose levels in a monitoring log provided. Patients should bring this monitoring log to scheduled visits and review with the treating physician. If a patient observes at home 2 or more fasting blood glucose measurements > 160 mg/dL (> 8.88 mmol/L) and/or 2 or more random blood glucose measurements > 200 mg/dL (> 11.01 mmol/L) (or a combination of the 2), or 2 or more positive urine glucose testing before their next scheduled clinic visit, they should call their health care professional (HCP), inform the study site, and schedule a visit as soon as possible with the treating physician. Treatment with metformin or anti-hyperglycemic agent of choice should be started (See [Figure 7-1](#)).
3. If fasting blood glucose > 160 mg/dL (> 8.88 mmol/L) and ≤ 250 mg/dL (≤ 13.87 mmol/L) on more than 2 occasions, start metformin or anti-hyperglycemic agent of choice. Patients should perform self-monitoring of blood glucose using finger stick blood testing or urine dipstick testing. Finger stick tests should be performed at home QD for at least 2 weeks, making note of time, fasted/fed state and glucose levels in a monitoring log provided. Patients should bring this monitoring log to scheduled visits and review with the treating physician.

[figure not shown]
4. If fasting glucose > 250 mg/dL (> 13.87 mmol/L), and the patient is not symptomatic, manage as for Step 3 above. If the patient is symptomatic, then hold CO-1686 and bring glucose under control acutely, if necessary using insulin with conversion to metformin or anti-hyperglycemic agent of choice once plasma glucose is controlled. Once patient is asymptomatic and deemed appropriate for additional therapy, CO-1686 may be re-introduced at a reduced dose, with concomitant metformin/anti-hyperglycemic agent of choice. Patients should perform self-monitoring of blood glucose using finger stick blood testing or urine dipstick testing. Finger stick tests should be performed at home BID for at least 2 weeks, before breakfast and before dinner, taking note of time, fasted/fed state and glucose levels in a monitoring log provided. Patients should bring this monitoring log to scheduled visits and review with the treating physician.

Metformin is contraindicated in patients with renal disease or renal dysfunction, among others, and use should follow the package insert and approved label. In order to minimize known gastrointestinal toxicity associated with metformin use, the extended release form and taking medication at bedtime are recommended to improve tolerability.²⁶ Additional recommendations to avoid gastrointestinal toxicity with metformin include starting treatment at a reduced dose (500 mg QD) for 72 hours, increasing to 500 mg BID for 72 hours, and if necessary, increasing up to 1000 mg BID. If plasma glucose is not adequately controlled with the regimen outlined above, then consider adding pioglitazone or an SGLT-2 inhibitor and consider consultation with an endocrinologist.

End-of-treatment

When CO-1686 is discontinued, need and use of anti-diabetic medications should be reassessed and patient treated appropriately.

Figure 7-1: Guidelines for Management of Hyperglycemia

Abbreviations: FG = fasting plasma or serum glucose (in mg/dL); HCP = health care practitioner; QD = once daily.

^a Guidelines intend to assist in managing patients that are non-diabetic at study start only.

^b Consider initiation of anti-hyperglycemic therapy, particularly for patients with symptoms of increased nausea, vomiting, decreased appetite, diarrhea, muscle cramps and fatigue.

^c For patients with a single elevation, fasting glucose can be repeated at the next regularly scheduled assessment.

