5 STUDY DESIGN

5.1 Overall Study Design and Plan

This is a Phase 2, single arm, open-label, dual cohort, multicenter study evaluating the safety and efficacy of CO-1686 administered PO BID to patients with previously-treated mutant EGFR NSCLC.

Patients will be enrolled into 2 cohorts. Cohort A will enroll approximately 125 eligible patients who are centrally confirmed T790M-positive and will be treated at 625 mg BID. Cohort B will be a continuation of the study and will enroll up to approximately 100 eligible patients who will be either centrally confirmed T790M-positive or T790M-negative. All patients in Cohort B will be treated at a starting dose of 500 mg BID. The priority for study enrollment will be for all T790M-positive patients to be enrolled into Cohort A first. Once Cohort A is complete, eligible T790M-positive patients will then be enrolled into Cohort B. All eligible T790M-negative patients will be enrolled into Cohort B.

All patients (for Cohort A and B) should have experienced disease progression while on treatment with the first single-agent EGFR-directed TKI (EGFR-TKI) therapy for advanced/metastatic NSCLC, and have had no intervening chemotherapy between EGFR-TKI and planned treatment with CO-1686. One line of chemotherapy prior to any EGFR-TKI treatment is permissible. The central laboratory will confirm that the patient's tumor harbors or does not harbor the T790M mutation using biopsy material obtained from either primary or metastatic tumor tissue within 60 days prior to dosing with study drug but after progression on EGFR-directed therapy.

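### The single TID ceiling of 1,125 mg/day in Protocol Section 7.4 lies above the Cohort B starting daily dose, and the text does not say how it fits with the no-escalation rule

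*Protocol*

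**What the plan says.** Protocol Section 7.3 gives the doses: "CO-1686 will be administered at a dose of 625 mg BID (Cohort A) or 500 mg BID (Cohort B". Section 5.1 confirms the second figure as a starting dose: "All patients in Cohort B will be treated at a starting dose of 500 mg BID".

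Section 7.4 then contains four rules that bear on this point.

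- A bar on escalation: "No dose escalation beyond the starting dose is allowed in either cohort". The Synopsis (Dose-Modification Criteria) and Section 5.1.2 repeat it.
- Reduction steps: "Dose reduction should be in increments of 125 mg BID", "with up to 2 dose reduction steps permitted in both cohorts".
- A possible change of schedule, in the same sentence as further reduction: "Any need for further dose reduction, or adjustment from a twice to 3 times daily (TID) dosing regimen should be discussed with the sponsor before" it is put into effect. The ceiling follows: "If a TID regimen is used, the total daily dose should not exceed 1,125 mg (i.e. not more than 375 mg TID".
- Re-escalation once an adverse event has resolved. This needs the sponsor's approval as well as discussion, and the section rules out escalation between visits.

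The Synopsis mentions the TID option but gives no ceiling. No passage gives a TID limit by cohort. Appendix C keeps the Section 7.4 dose-modification criteria in force during the Extension Phase.

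**The concern.** The ceiling is given once, as if it suited both cohorts, but the cohorts start at different daily doses. A site treating a Cohort B patient could stay within the TID sentence and still give more drug per day than the patient started on. The first sentence of the same section appears to forbid that.

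What is at stake is the safety meaning of a stated dosing limit. A limit that fits one cohort and not the other leaves the site and the sponsor to work out which rule applies, patient by patient. A second gap concerns patients who have already been reduced. A move to TID can raise their daily total, yet the wording for a TID change asks for discussion, while the wording for re-escalation asks for approval.

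**Working it through.** **Inputs**

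- Cohort A start, 625 mg BID (Section 7.3).
- Cohort B start, 500 mg BID (Sections 5.1 and 7.3).
- Reduction step, 125 mg BID, with up to two steps (Section 7.4).
- TID ceiling, 375 mg per intake (Section 7.4).
- Tablet strengths: "125 mg strength is a round tablet and 250 mg strength tablet is an oval tablet" (Section 7.1). One of each makes 250 + 125 = 375 mg, so the ceiling regimen can be dispensed.

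**Formula:** daily dose = mg per intake × intakes per day.

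**The plan's own figure:** 3 × 375 = 1,125 mg/day. This reproduces exactly; the sum in Section 7.4 is correct.

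**Ceiling against each BID level**

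| Cohort | BID dose | Daily total (mg) | 1,125 minus daily total (mg) | Relative difference |
|---|---|---|---|---|
| A, start | 625 mg | 2 × 625 = 1,250 | −125 | −125/1,250 = −10% |
| A, one step down | 500 mg | 2 × 500 = 1,000 | +125 | +12.5% |
| A, two steps down | 375 mg | 2 × 375 = 750 | +375 | +50% |
| B, start | 500 mg | 2 × 500 = 1,000 | +125 | +125/1,000 = +12.5% |
| B, one step down | 375 mg | 2 × 375 = 750 | +375 | +375/750 = +50% |
| B, two steps down | 250 mg | 2 × 250 = 500 | +625 | +625/500 = +125% |

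The two starting rows bear on the starting-dose rule: the ceiling is compatible with it in Cohort A and exceeds it in Cohort B. The four reduced rows bear on a different rule, re-escalation, and there the question arises in both cohorts.

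**Does the choice of unit matter?** Per intake, 375 mg is below both 625 mg and 500 mg, and no conflict appears. Per day, 1,125 mg is above 1,000 mg, and it does. The protocol does not say which unit its starting-dose rule uses. The ceiling is itself written as a total daily dose, so daily totals are the fairer comparison.

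**The case against.** The strongest reply is that both rules can be obeyed together. The TID sentence sets a maximum; it does not tell anyone to give 1,125 mg. A reader who applies every sentence of Section 7.4 would let the stricter one bind, and the sponsor is to be consulted before any TID change. This stands in part: the protocol does not instruct escalation in Cohort B, and consultation makes a breach less likely. It does not close the gap, because the text gives no order of precedence and does not define the starting dose by intake or by day.

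Several stronger readings are tempting, and the documents do not support them.

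- *The ceiling is the only number the sponsor discussion has to work with.* Section 7.4 also gives the no-escalation rule, the step size, the step limit and each cohort's first reduced dose.
- *The 50% rise from 375 mg BID to 375 mg TID breaks the starting-dose rule.* That rule concerns the starting level. A rise from a reduced level belongs to the re-escalation rule; what is missing is whether a TID change counts under it.
- *TID is meant for patients who do not tolerate the drug, and will raise their exposure.* The protocol gives no reason for a TID change; the motive is inferred from where the sentence stands. Section 3.4.3 reports single-dose and BID pharmacokinetics only, so the point here is about dose, not measured exposure.
- *A dose comparison between the cohorts is compromised.* No formal comparison of A with B is planned. Cohort B is sized for a one-sample test in about 40 evaluable T790M-negative patients, and its other purpose is to describe the 500 mg BID dose.
- *About 100 patients are at risk.* That is the planned Cohort B enrolment. Under Appendix C no one further is enrolled, only patients still on treatment are covered, and dosing is described there as twice a day. The number ever moved to TID is not given.

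**Conclusion.** The inconsistency is real and narrow. Measured as daily totals, the one TID ceiling in Section 7.4 fits Cohort A, at 125 mg/day below its start, and does not fit Cohort B, at 125 mg/day above its start. The conclusion rests on two things: that the ceiling applies to both cohorts, since none is named, and that the starting dose is compared per day, as the ceiling is. If the sponsor meant a per-intake comparison, the numerical conflict disappears, but the protocol would need to say so.

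The status of a TID change in a patient already reduced is a separate omission, and it holds whichever unit is used for the starting-dose rule.

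The practical reach is limited to patients remaining on treatment. The point still merits correction, because it concerns a dosing limit and Section 7.4 continues to apply in the Extension Phase. It does not affect the sample size, the primary endpoint or any planned test.

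**What to change.** Reconcile Section 7.4 with the Synopsis (Dose-Modification Criteria), Section 5.1.2 and Section 7.3, so that the TID limit, the no-escalation rule and the re-escalation rule agree. The revised text should state:

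1. whether the starting dose in the no-escalation rule is per intake or per day;
2. which limit governs a TID schedule in each cohort;
3. whether a TID change that raises the daily total of a patient already reduced is a re-escalation, and so needs approval.

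The values and rules are for the sponsor to decide; none is proposed here. The cost is a sentence or two in Section 7.4, with matching wording in the other places.

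Optionally, the by-dose safety summaries could flag any patient whose total daily dose exceeded the cohort's starting daily dose. Protocol Section 11.2.5.1 counts reductions, delays and interruptions, so such an increase has no category at present. The flag would be one derived variable from dosing data already collected; the patient diary records the date, time and dose of each administration (Section 9.5.6).

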3.1.1 Extension Phase

The purpose of this protocol amendment (Amendment 5) is to add a new Extension Phase to allow patients to continue on study but to avoid unnecessary collection of data that will no longer be analyzed or required for regulatory purposes, whilst maintaining an appropriate level of safety monitoring. A new schedule of assessments for the Extension Phase as well as a complete description of procedures is provided in [Appendix C](#). This schedule replaces all schedules of assessments in [Section 9](#) and should be followed for all patients.

In addition, Amendment 5 ([Appendix C](#)) also introduces the availability of NAT2 testing for patients, an indirect indicator of the likelihood of developing hyperglycemia and QTc prolongation. The availability and disclosure of this information to the patient's treating physician will not affect the monitoring and associated treatment guidelines for these adverse events.

For patients who wish to continue rociletinib treatment post progression, it is important that a full exploration of alternative treatment options between patients and their treating physicians takes place.

Investigators and their staff are directed to the current Investigator's Brochure for the most current efficacy and safety data, in which integrated summaries of the latest available data can be found and supersedes all safety and efficacy data in this protocol.

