9.5.1.2 Clinical Laboratory Investigations

Blood will be sent for analysis to a central laboratory for all cycles Day 1 visits, but must also be analyzed by a local laboratory to inform patient treatment decisions. Local hematology results must be reviewed by the investigator prior to start of CO-1686 administration. Additional tests may be performed at the investigators discretion. The panels of laboratory tests to be performed are shown below:

Hematology: Hemoglobin, hematocrit, WBC and differential (with ANC), reticulocyte count, and platelet count per the schedule of evaluations at Screening, during treatment, and at the End-of-Treatment Visit. Hematology results must be reviewed by the investigator prior to the start of treatment with PO CO-1686.

Patients known to require concomitant therapy with anticoagulant therapy such as warfarin should have international normalized ratio (INR) monitored at Screening and during the study.

Fasting Glucose: Must be measured following an 8-hour fast (no food or liquid other than water) at Screening, C1D1, C1D4, C1D8, C1D15, C2D1, C2D15 and every Cycle *N* D1 thereafter and at the End-of-Treatment Visit, also if clinically indicated on study. Fasting glucose will be measured as part of clinical chemistry panel (see below) on all cycles Day 1 visits, and measured individually (local lab) C1D4, C1D8, C1D15, and C2D15.

Clinical Chemistry: Total protein, albumin, creatinine, BUN or urea, total bilirubin, alkaline phosphatase, ALT, AST, total cholesterol, fasting glucose, sodium, potassium, magnesium, chloride, calcium, and phosphorus per the schedule of evaluations at Screening, during treatment, and at the End-of-Treatment Visit. Serum levels of AAG will be determined on PK sampling

days. HbA1c will be measured at Screening and Day 1 of every other cycle (Cycle 3, 5, 7 etc.) while the patient is on study.

Urinalysis: Performed on freshly voided clean sample by dipstick for protein, glucose, blood, pH, and ketones per the schedule of evaluations. If dipstick findings are abnormal, then a microscopic evaluation will be performed to assess the abnormal findings. Urinalysis will be performed at Screening only.

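### Section 7.4 gives inconsistent counts for starting glucose-lowering therapy: two home fasting readings above 160 mg/dL in Step 2, but at least three in Step 3, the higher-glucose band

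*Protocol*

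**What the plan says.** The rules are in Protocol Section 7.4, under management of hyperglycemia.

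- **Status of the steps.** "Whilst the blood glucose thresholds for intervention outlined below should be followed, management of individual patients should be based on local practices" and on the treating physician's judgment. A footnote to Figure 7-1 limits the guidance to patients who were not diabetic at study start.
- **Step 2 (fasting glucose 125 to 160 mg/dL).** Daily home testing begins and drug treatment is to be considered straight away. The count rule opens: "If a patient observes at home 2 or more fasting blood glucose measurements > 160 mg/dL". Two or more random readings above 200 mg/dL, a mix of the two kinds, or two or more positive urine tests also qualify. The patient then arranges a visit, and "Treatment with metformin or anti-hyperglycemic agent of choice should be started".
- **Step 3 (above 160 and up to 250 mg/dL).** The rule is "on more than 2 occasions, start metformin or anti-hyperglycemic agent of choice". Daily home testing is mentioned next, without saying when it begins. The text does not say where the counted readings are taken, and it has no clause about considering treatment earlier.
- **Step 4 (above 250 mg/dL).** For this level "and the patient is not symptomatic, manage as for Step 3 above".
- **Figure 7-1, footnote c.** "For patients with a single elevation, fasting glucose can be repeated at the next regularly scheduled assessment".
- **Testing schedule.** Section 9.5.1.2 lists the fasting glucose visits and adds "also if clinically indicated on study". Section 3.1.1 says of the Appendix C extension schedule: "This schedule replaces all schedules of assessments in" Section 9. The extension schedule measures fasting glucose on Day 1 of each 28-day cycle.

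Appendix C keeps the Section 7.4 hyperglycemia guidance in force for ongoing patients, asks that departures be agreed with the sponsor beforehand, and closes enrollment.

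**The concern.** The same drug, for the same complication, is started at two different counts of the same kind of reading. A patient who enters at 125 to 160 mg/dL and then records two home fasting values of, say, 170 mg/dL should be treated under Step 2. Those values also lie in Step 3's band, and Step 3 asks for a third. A patient who enters above 160 mg/dL meets only the stricter rule, with no stated start for home testing. The order is the reverse of what one would expect, since the higher band carries the higher bar.

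At stake is the handling of a common toxicity of this drug. In the pooled rociletinib data in Appendix C, Table 2, 121 + 65 + 17 = 203 of 635 patients (32%) had at least one post-baseline glucose value above 250 mg/dL. That figure is not specific to this trial and does not give the share of patients whom the wording affects. A site that follows the words could wait for a third reading in a patient without symptoms.

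**Working it through.** No statistical figure in the plan depends on this point, so the check compares the two rules and then works out what the count adds in days.

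**1. The rules side by side.** Let k be the number of fasting readings above 160 and up to 250 mg/dL.

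| k | Step 2 (k ≥ 2) | Step 3 (k > 2) |
|---|---|---|
| 1 | count not met | count not met |
| 2 | start | count not met |
| 3 or more | start | start |

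The rules differ only at k = 2. With Step 3 changed to k ≥ 2, the conflict disappears.

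**2. Timing if home readings count.** Assume that day 0 is the clinic value, home tests are daily from day 1, and every home value is above 160 mg/dL.

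- Step 2: the clinic value (125 to 160) is not counted. Day 1 gives k = 1 and day 2 gives k = 2, so treatment starts on day 2.
- Step 3: the clinic value gives k = 1, day 1 gives k = 2 and day 2 gives k = 3, so treatment starts on day 2.
- Step 3 with a two-reading rule that counts the clinic value: k = 2 on day 1.

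The difference is 2 − 2 = 0 days against Step 2, and 2 − 1 = 1 day against the two-reading rule.

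**3. Timing if only scheduled clinic readings count.** In the extension phase the readings fall on days 0, 28 and 56. A two-reading rule on the same visits is met on day 28 and Step 3 on day 56. The count alone adds 56 − 28 = 28 days.

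**4. The Section 9 schedule, now replaced.** Nominal days were 4, 8, 15, 29, 43, 57, 85 and 113. The added wait is the third reading minus the second:

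| First high value | Calculation | Added days |
|---|---|---|
| C1D4 | 15 − 8 | 7 |
| C1D8 | 29 − 15 | 14 |
| C1D15 | 43 − 29 | 14 |
| C2D1 | 57 − 43 | 14 |
| C2D15 | 85 − 57 | 28 |
| C3D1 | 113 − 85 | 28 |

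**5. A unit check in passing.** The printed conversions give 8.88/160 = 0.0555 and, in SAP Section 11.2, 13.875/250 = 0.0555 (taking that cut-off as 250 mg/dL). Step 2's figure for 200 mg/dL gives 11.01/200 = 0.05505. With the common factor it would be 200 × 0.0555 = 11.10 mmol/L. Read literally, 11.01 mmol/L is 11.01/0.0555 = 198.4 mg/dL, so the slip leads to slightly earlier action.

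**The case against.** The best counter-argument is that the two counts start from different places. Step 2 needs a clinic value of 125 to 160 mg/dL plus two home values above 160, which is three abnormal readings. If the clinic value is Step 3's first occasion, Step 3 also needs three. The timing above bears this out: both are met on day 2. This stands as a reason why the practical difference may be nil. It does not reconcile the wording, because Step 3 never says that home readings count or that home testing has begun.

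Second, the steps leave individual management to local practice and clinical judgment, unscheduled fasting glucose is allowed, and Section 7.4 also speaks of early treatment in patients with symptoms and of starting metformin together with the study drug. A physician may treat after one or two readings and stay within the guidance. This stands and lowers the severity.

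Third, the body of Figure 7-1 cannot be seen in the text reviewed and may settle the count. Footnote c lets only a single elevation wait for the next scheduled test, which leans toward a two-reading rule. The figure might therefore resolve the matter, but the written steps would still disagree with each other.

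Two stronger readings are tempting. A reader might infer that the protocol delays treatment by four weeks in its sicker patients. The documents do not support that. The 28-day case needs a patient without symptoms, no home readings, no unscheduled test and no use of judgment. Section 7.4 also says that onset is generally in the first 3 weeks, and no new patients are entering. A reader might also infer from Step 4 that patients without symptoms above 250 mg/dL must collect three readings before treatment. The more natural sense is that only Step 3's actions carry over, so Step 4 needs clarifying and is not a demonstrated fault.

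**Conclusion.** The inconsistency is real and sits in the text of Section 7.4: two home readings in Step 2, at least three of unstated origin in Step 3. It is a low-severity patient-safety point in guidance that permits physician judgment. It touches no endpoint and changes no planned analysis.

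The added wait runs from 0 days (against Step 2, home readings counted) through 1 day (against a two-reading rule that counts the clinic value) to 28 days (extension-phase Day 1 readings only). The low end assumes daily home testing from the day after the first high value. The high end assumes that every reading is scheduled and that nobody acts in between. The documents do not give the share of patients in either situation, and they do not show that any delay occurred. The point is still live because Appendix C keeps Section 7.4 in force for patients on treatment. The 11.01 mmol/L figure is a clerical slip and adds no weight.

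**What to change.** In Section 7.4:

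1. Change the Step 3 count to *2 or more occasions (home or clinic)*.
2. State in Step 3 that home self-monitoring starts at the first fasting value above 160 mg/dL.
3. State in Step 4 that patients without symptoms above 250 mg/dL need no higher count than Step 3's.
4. Bring Figure 7-1 and its footnote c into line with these rules.
5. As a clerical correction, print 11.10 mmol/L for 200 mg/dL in Step 2.

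The cost is wording in one section and one figure, with no extra scheduled visits. The downside is slightly earlier home testing and metformin use in some patients, with the gastrointestinal effects that Section 7.4 already describes and offers ways to limit.
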